Descriptive analyses will be conducted to characterize high risk PCa census tracts compared to lower risk census tracts. Mapping the high risk census tracts will help us to determine how they are distributed within and around pre-defined Philadelphia neighborhoods (commonly used community names for each section of the city, Figure 2.) Those Philadelphia neighborhoods will become the target

neighborhoods for aims 2 and 3. Continuous variables will be analyzed with t-tests (or nonparametric alternative tests for variables without normal distributions) and categorical variables will be analyzed with frequency tables and chi square tests or Fisher's exact tests if any expected cell frequencies are small. Patient-level and neighborhood variables will be summarized for comparisons between high risk and lower risk neighborhoods to highlight factors that may be central topics of focus groups and intervention development. Correlations will be computed to examine the relationship between percent of cases with advanced disease and prostate-specific mortality rates. Regression modeling will allow us to determine significant trends in PCa incidence and mortality over time with and without adjustment for covariates such as the prevalence of risk factors including older age at diagnosis, African American residents and low neighborhood SES. We will also use the EpiQMS tool provided on the PA Department of Health website to determine age-specific incidence and mortality rates for Philadelphia. Generating maps of these data along with maps showing highest prevalence of PCa screening (CHDB data) will indicate where should target our focus groups and interventions for aims 2 and 3.

B2.f. Designation of Neighborhoods for Study Condition

Based on the GIS mapping results, the four neighborhoods in Philadelphia with the highest rates of late-stage PCa will be chosen to serve as study sites. Study condition (intervention or control) will be designated at the neighborhood level. Therefore, two of the sites will be designated as intervention neighborhoods and two will be designated as control neighborhoods. All men who live in the same neighborhood will receive the same intervention. All efforts will be made to ensure that the designations are done in a way that Intervention and Control neighborhoods are not geographically adjacent to each other, to avoid contamination of study messages among participants.

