It is anticipated that the small-group educational sessions will occur at sites that frequently draw middle-aged and senior men from the target population in each pre-selected neighborhood. This will include churches, barbershops, recreational centers, community development corporations, employment centers, and neighborhood restaurants. [54] MEE will identify and engage these types of establishments in each target neighborhood by drawing upon its vast network of community partners in Philadelphia. MEE will also conduct phone book and Internet searches to identify potential recruiting locations and sites for educational sessions. They will introduce the study to the leadership of each location and explain the requirements of holding a study intervention session at their facility. MEE will create informational packets for interested study sites to aide in the discussion. The only requirement of a study site is to provide a space for which the research team can conduct a study session. Recruitment for the study session will be done by the study team, although a site is welcome and encouraged to invite eligible men who it has contact with. Sites may agree to hold more than one session, provided that the study team leadership feels that an adequate number of participants can be recruited at that site. Study sites will be compensated based on the number of study sessions that occur on their premises.

B.4. Aim 3: To test the impact of the targeted intervention on levels of knowledge, anxiety, and informed decision making about PCa screening

B.4.a. Participant Recruitment

MEE will develop an e-mail blast, flyers for study site partners and recruiting information to recruit eligible men from the neighborhoods for participation. If these efforts need to be augmented, MEE will also conduct canvassing of key transportation corridors in the selected Philadelphia neighborhoods, to recruit potential study participants. The study team will also draw upon the community contacts and resources of the Penn Center for Community Health Workers to identify men eligible for participation. The goal is to enroll 200 men in the study over a period of 18 months. We anticipate, based on our previous experience in community-based research, that we will have to screen about 10 times that number, or about 2000 men, to reach our study recruitment goals.

B.4.b. Study Eligibility

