Men from both groups who decide that they want to be screened for prostate cancer will be linked with medical care at Thomas Jefferson University Hospital (TJUH) if the participant does not have a primary care physician for medical care. Participants will be encouraged to contact their primary care physician for screening, or in the absence of a primary care physician, [name] at TJUH, a study co-investigator and oncologist who specializes in high-risk populations, will provide screening at TJUH. In addition, [name] will care for any male who completes screening and requires follow-up medical care based on his test results. A letter of support

from [name] attesting her commitment to provide thorough medical care for any male who screens for prostate cancer as a result of this project is included in the application.

B.4.d. Analysis Plan

Since Aim 3 will not be addressed by a randomized trial design and we anticipate clustering of observations from the same neighborhood, linear and generalized linear mixed models having random intercepts corresponding to neighborhood will be applied to test the quantitative hypotheses. This approach will allow us to account for the correlation between participants from the same neighborhood and adjust the parameters of interest for potential confounding variables. Potential confounders will be identified and choices about specific models will be made after computing descriptive statistics to compare the distributions and identify imbalances of study variables between the groups (i.e., intervention vs. control) or variables (e.g., the number of barriers to screening) of interest for the given hypothesis. If substantial clustering also exists at the site level, this hierarchical correlation will also be incorporated into the models.

A sub-aim of this study will be to determine whether there are differences in results based on where the intervention is implemented. As neighborhoods often attract certain demographics of the population, so do various gathering places for men. Some gathering places may prove to be better for achieving the goals of this study – increasing PCa knowledge and shared decision making about PC a screening among high risk men. During aim 2, the content will be optimized for each setting and suggestions will be made for future interventions in these settings.

B.4.e. Power Analysis

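### Section B2.f does not say how condition is assigned to the four neighborhoods, although a random draw is available at essentially no cost

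*Combined protocol and SAP*

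**What the plan says.** B2.f settles which neighborhoods enter by mapping and ranking: "the four neighborhoods in Philadelphia with the highest rates of late-stage PCa will be chosen to serve as study sites". It fixes the level of assignment ("Study condition (intervention or control) will be designated at the neighborhood level") and the ratio: "two of the sites will be designated as intervention neighborhoods and two will be designated as control neighborhoods". The one rule on which neighborhood goes where is an effort to ensure that "the designations are done in a way that Intervention and Control neighborhoods are not geographically adjacent to each other", intended to limit contamination. The section names no mechanism, no decision-maker and no time of designation.

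B.4.d opens with "Since Aim 3 will not be addressed by a randomized trial design" and does not say why. Its response is analytic: mixed models with a random intercept for neighborhood, adjustment for confounders to be identified after the groups have been described, and a site-level term if clustering there proves substantial.

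On session venues, B.3.e says: "This will include churches, barbershops, recreational centers, community development corporations, employment centers, and neighborhood restaurants". It adds that "MEE will identify and engage these types of establishments in each target neighborhood by drawing upon its vast network of community partners in Philadelphia". No quota or matching by condition is set. B.4.d observes that "As neighborhoods often attract certain demographics of the population, so do various gathering places for men" and makes intervention setting a sub-aim.

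**The concern.** Ranking decides which four neighborhoods take part. It does not decide which two receive the prostate-specific program. By the time that choice is made, the team may already hold neighborhood-specific information from the Aim 2 focus groups (B.3.c) and may know where its community contacts are strongest (B.3.e). Nothing in the plan requires designation to come first. If the choice leans, even unintentionally, toward neighborhoods where men start better informed or are more receptive, that difference is counted as intervention effect.

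Adjustment is a weak remedy. Four neighborhoods leave 2 degrees of freedom between neighborhoods after the condition contrast, so at most one neighborhood-level covariate can be added with any left over. The random intercept widens the standard error but does not remove a systematic difference between the two pairs.

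Venue raises a smaller version of the same question. If venue types differ between conditions, the men differ too, and condition and setting become hard to separate.

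**Working it through.** **1. The plan's own power figure.** Inputs from B.4.e: difference 0.8, SD 1.5, n = 200, type I error 0.05 (taken as two-sided), intra-neighborhood correlation (ICC) 0.005 to 0.01, and k = 4 to 10 neighborhoods per group. With m = 200/(2k) men per neighborhood, the design effect is DE = 1 + (m − 1) × ICC. The noncentrality is 0.8 / (1.5 × √(2 × DE/100)), referred to a noncentral t with 2(k − 1) df.

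- k = 4, ICC 0.01: m = 25, DE = 1.24, power 80.4%.
- k = 10, ICC 0.005: m = 10, DE = 1.045, power 93.7%.

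This reproduces the stated 80% to 94%. With the two neighborhoods per condition of B2.f, m = 50 and df = 2. DE is 1.245 at ICC 0.005 and 1.49 at ICC 0.01, and power is 45.6% and 40.3%. A random draw does not change these values.

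**2. Between-neighborhood SD.** σ_b = √ICC × 1.5.

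**3. Worst-case designation.** For four independent normal neighborhood effects, the expected ordered values are ±1.029 and ±0.297 SDs. The top two average (1.029 + 0.297)/2 = 0.663 and the bottom two −0.663, so the expected gap is 1.326 σ_b.

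**4. Random draw.** Each neighborhood is equally likely to fall in either condition, so the expected signed gap is zero. The difference between two means of two has SD σ_b × √(1/2 + 1/2) = σ_b. Its expected absolute size is √(2/π) × σ_b = 0.798 σ_b.

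| | ICC 0.005 | ICC 0.01 |
|---|---|---|
| σ_b (points) | 0.106 | 0.150 |
| Worst-case expected gap, 1.326 σ_b | 0.141 | 0.199 |
| as share of 0.8 | 18% | 25% |
| Expected absolute chance gap after a draw, 0.798 σ_b | 0.085 | 0.120 |
| as share of 0.8 | 11% | 15% |

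**5. Is a draw compatible with non-adjacency?** Four neighborhoods form three pairings, hence C(4,2) = 6 labelled splits. Non-adjacency is symmetric: if a pairing qualifies, it qualifies with the labels swapped. So whenever any split is acceptable, at least two are, and a coin flip is possible. Under strict non-adjacency the count is 0, 2 or 6, because any two of the three pairings together involve all six between-neighborhood borders. If two pairings qualify, none of the neighborhoods adjoin and the third qualifies as well. The map is not available here, so the actual count is unknown.

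**The case against.** The strongest reply is that the plan is open about this. It says that Aim 3 is not randomized, and for that reason it adopts mixed models and confounder adjustment. It also spreads recruitment evenly over the four neighborhoods. Knowledge is measured before the session (B.4.c), so a difference in starting level would be visible and could be adjusted for. The 18% to 25% describes the least favorable pairing and direction, and a draw would still leave roughly 60% of that gap (0.798/1.326) as chance imbalance. With only six splits, the smallest two-sided randomization p-value is 2/6, so a draw cannot by itself support a 5% test. The deeper limitation is two clusters per condition, which a draw does not touch.

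Most of this stands, and it limits the point without removing it. This is a disclosed design weakness, not a hidden error. Baseline adjustment would help with starting level, but B.4.d does not commit to it, and it would not address differences in receptivity or retention. Chance imbalance with known expectation zero is also preferable to imbalance of unknown direction. Nothing in the documents rules out a draw.

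On venues, the reply is stronger. B.3.e seeks the same kinds of establishment in every target neighborhood, so a reader who infers that one condition will be church-heavy and the other barbershop-heavy goes beyond the text. Identical mixes may not be attainable. A formal condition-by-venue interaction over six types and two conditions would average about 17 men per cell (200/12), too few to be informative.

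**Conclusion.** The point holds as a design weakness that should be corrected. The rule for assigning condition is missing, and a better method is available that costs essentially nothing. At the plan's own ICC and SD, the worst-case expected spurious gap is 0.14 to 0.20 points (18% to 25% of 0.8). A draw brings the expected bias to zero but leaves an expected absolute chance gap of about 0.08 to 0.12 points.

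These sizes assume independent, normally distributed neighborhood effects and no baseline adjustment. They are on the 10-point scale of the cited study in B.4.e, whereas this trial uses a 17-item measure (B.4.c).

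Three stronger readings are tempting, and the documents do not support them:

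- **That the team hand-picks the neighborhoods or means to favor receptive ones.** The four come from registry ranking. Discretion over condition is inferred from the absence of a mechanism, and no text suggests favoritism.
- **That designation is the largest avoidable source of bias.** No comparison with other sources can be made from the documents.
- **That a draw would make the comparison sound.** Power with two neighborhoods per condition stays at 40% to 46%, and condition remains largely confounded with neighborhood.

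**What to change.** **B2.f.** Once the four neighborhoods are fixed and before any venue is approached, list the 2-versus-2 splits that meet the non-adjacency preference and have the statistician draw one at random and record it. If only one pairing qualifies, randomize which pair receives the intervention. If none qualifies, take the pairing with the least adjacency and randomize between its two labellings.

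**B.4.d.** Replace the statement that the design is not randomized with a description of the draw. Keep the mixed model and covariate adjustment, since four clusters leave chance imbalance.

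**B.3.e and the setting sub-aim (secondary).** Aim for a similar mix of venue types across conditions where feasible, report the mix by condition, and label the setting comparison exploratory. No interaction test need be required.

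**Cost.** The draw needs no extra participants, venues or visits; the team gives up only the freedom to choose which neighborhoods receive the intervention. The venue step costs some flexibility in site recruitment, which is why it is worded as an aim. Neither change addresses the number of neighborhoods per condition, which needs separate attention.

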B.3. Aim 2: To develop a targeted PCa screening intervention for the high risk neighborhoods using a mixed-methods approach.

The study team will develop a behavioral intervention informed by neighborhood-level data and the health experiences of men living in the pre-selected neighborhoods. The intervention will be developed to be culturally sensitive to the context of high risk urban populations using data from previous research, local context, and pilot testing to refine intervention components. [9]

B.3.a.Theoretical Framework

The Theory of Planned Behavior (TPB) posits that an individual's intention to perform a given behavior, in this case one's intention to be screened for prostate cancer, is based on one's attitudes toward the behavior (positive or negative evaluation of performing the behavior), subjective norms (perception of the social pressures to perform or not perform the behavior), and one's perceived behavioral control (perception of the ability to perform the behavior. [10] Behavioral beliefs produce a favorable or unfavorable attitude toward the behavior; normative beliefs result in perceived social pressure or subjective norm; and control beliefs give rise to perceived behavioral control. The TPB is a useful model for predicting a wide range of behaviors and behavioral intentions [11] and has been used in the context of prostate cancer education in the past. [12-14] Therefore, the messages in the health education curriculum will aim to increase positive attitudes towards prostate cancer screening, create favorable subjective norms related to screening, and improve perceptions of behavioral control over the screening decision.

B.3.b. Development of Study Materials

MEE's Creative Team will develop a series of educational materials for use during participant recruitment and the health education sessions. These materials may include: a summary presentation to outline the project and its incentives to participants; a one-page, formal Partnership Agreement signed by each participating study site; posters and "Ask Me About Prostate Health" buttons that can be prominently displayed and worn by members of partner sites, helping to publicize the project; a customized, user-friendly curriculum booklet for the small group education sessions; and a project Facebook page and Website.

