The training manual will be the guide for the health educator training sessions. [name] will lead the training sessions with assistance from Drs. [name] and [name] and the Penn Center for Community Health Workers as necessary. It is anticipated that each health educator will attend 3 sessions, each 3 hours long. The first session will cover topics in men's health, with a special emphasis on prostate cancer and screening. The second session will include study-specific information such as the study aims and details of the intervention, the informed consent process, a review of the study surveys, and roles and responsibilities of a health educator. The third session will be entirely interactive and will allow the health educators to practice with others and receive feedback from study staff. There will also be an opportunity for the educators to ask questions and receive clarifications. At the end of the third session, it is our expectation that the health educators would be sufficiently trained and competent to deliver the intervention. However, if study staff determine that an educator needs more training, opportunities will be made to provide additional training.

B.3.e. Recruitment of Study Sites

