Study Intervention: Men who live in the Intervention Group Neighborhoods: After obtaining informed consent and administering the baseline survey, the health educator will show the short introductory video on a tablet computer. Then, the educator will use the curriculum booklet, one given to each participant, to review general information about the prostate gland, prostate incidence and development, risk factors, screening options, screening guidelines and the importance of repeat screening.[20] The educational session is meant to be interactive, with men feeling comfortable to ask questions and engage in a discussion with the educator and the other men at the session. Men Who Live in the Control Group Neighborhoods: After obtaining informed consent and administering the baseline survey, the health educator will show the short introductory video on a tablet computer. Then, the educator will use the curriculum booklet, one given to each participant, to review topics about health promotion actions related to diet, exercise, tobacco, general cancer screening and cardiovascular risk. The educational session is meant to be interactive, with men feeling comfortable to ask questions and engage in a discussion with the educator and the other men at the session. It is anticipated that the educational sessions for both groups will last about 15 minutes.

Post-Survey(s): Immediately following the intervention, men will complete a brief paper-and-pencil endpoint survey. The majority of items on the baseline survey, except for the demographic and contact information, will be repeated on the endpoint survey. Additionally, the study research assistant will call each enrolled participant at 1 month and 4 months after their enrollment date to administer the same endpoint survey. Participants who are not reached by telephone will be contacted by mail and by email to attempt to retain the maximum number of participants over time.

Participant Compensation: Participants will be compensated \$25.00 after completing the endpoint survey on the day of the intervention and \$25.00 for the completion of each follow-up survey.

Referral to Screening

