The target sample size is $n=200$ men. Since we anticipate 20% attrition, we will recruit and consent 240 evenly distributed across each of the 4 neighborhoods. In a local population similar to our target population, a previous prostate cancer screening decision making study [21] found that, compared to standard intervention controls, their decision support enhanced intervention lead to a 0.8 point increase ($SD = 1.5$) in knowledge on a 10-point scale. Assuming this in our target population, a type I error rate of 0.05, an intra-neighborhood correlation of 0.005 to 0.01, and that 4 to 10 neighborhoods will be sampled per group, the planned study should have approximately 80% to 94% power to detect this difference. In a similar prostate cancer screening shared decision making article [22], investigators found that their intervention lead to a 22% reduction ($SD = 0.15$) in prostate screening. Making similar assumptions as for the knowledge endpoint, we may be somewhat underpowered for detecting this difference in screening rates as the expected power would be approximately 50% to 67%. However, the primary goal is to increase knowledge about screening so that each man will make an informed decision taking into account his risk factors and personal preferences.

B.4.f. Results Dissemination

The study results will be disseminated to the neighborhood at the end of the project by multiple methods. Town hall meetings will be held in the targeted neighborhoods to explain the goals of the study and to provide a summary of results and additional PCa education to the community at-large. Next steps will be discussed, as well as ways to improve, sustain and expand targeted educational interventions around the Philadelphia region. Project newsletters and brochures will be made available to be shared with family and community members. The video developed during aim 2 for educational purposes will be shared at the town halls and will be made available on the internet for public education.

C. Potential Problems and Alternative Approaches

C.1. Geocoding

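### Prostate-branded publicity is not assigned by study condition, and keeping neighborhoods apart does not control it, so the 1- and 4-month contrasts may be narrowed or confounded

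*Combined protocol and SAP*

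**What the plan says.** B2.f of the combined protocol and SAP assigns condition by neighborhood, two intervention and two control. It asks that the two kinds not be adjacent, "to avoid contamination of study messages among participants". No other safeguard against contamination is given.

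B.3.b lists materials for recruitment and for the sessions. The list is worded as optional. It includes "posters and 'Ask Me About Prostate Health' buttons that can be prominently displayed and worn by members of partner sites", and one Facebook page and website for the project. Nothing in the list is tied to a condition. B.3.e has partner sites engaged in every target neighborhood, so control neighborhoods have them too. By contrast, B.3.b does separate the two videos by group.

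B.4.c has the control session review "topics about health promotion actions related to diet, exercise, tobacco, general cancer screening and cardiovascular risk". It does not say whether prostate screening falls inside that topic. On educator training, B.3.d states: "The first session will cover topics in men's health, with a special emphasis on prostate cancer and screening". No separate training for control sessions is described.

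Knowledge, attitudes, norms, decisional conflict and intention are measured at baseline. Most items are repeated directly after the session and again at 1 and 4 months (B.4.c).

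**The concern.** The plan treats leakage of study messages as a threat, but guards only against men in neighboring areas talking to each other. Posters, buttons and a web page reach men by a different route.

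Neither way of using this publicity is clean:

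- **In all four neighborhoods.** Control men may meet prostate messages during the four months in which they are followed. The intervention is meant to act partly through subjective norms (B.3.a). Buttons worn by familiar people at a church or barbershop work on that same pathway and invite conversation, even though they teach little. This would tend to shrink the difference between conditions.
- **In intervention neighborhoods only.** Intervention men would respond to a prostate message and control men to something else. Condition is not randomized, so the groups could differ in prior interest, and the direction of the resulting bias is unknown. B.4.b also excludes men screened in the past 12 months, and B.4.a enrolls over 18 months. Publicity that prompts screening could therefore change who remains eligible in one condition.

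At stake is whether a difference in knowledge or informed decision making (Hypotheses 3a and 3c), or its absence, can be attributed to the targeted session.

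**Working it through.** **What each safeguard covers**

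| Route of exposure | Non-adjacency (B2.f) | Baseline survey (B.4.c) | Same-day endpoint (B.4.c) |
|---|---|---|---|
| Publicity seen before enrollment | No | Yes, if the model uses the baseline score | Yes, through baseline |
| Publicity seen between session and 4 months | No | No | Yes, already measured |
| Prostate content arising in a control session | No | No | No |

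The 1- and 4-month contrasts are therefore the exposed ones. The same-day contrast is open only through what is said in the control session, which the plan leaves unspecified. B.4.d selects confounders after imbalances have been examined, so use of the baseline score is possible but not fixed.

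**The plan's own power figure**

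Inputs from B.4.e: "a type I error rate of 0.05", "0.8 point increase ($SD = 1.5$) in knowledge on a 10-point scale", "an intra-neighborhood correlation of 0.005 to 0.01" and "4 to 10 neighborhoods will be sampled per group", with 200 men (100 per group). Sidedness is not stated; two-sided is assumed.

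With k neighborhoods per group, m = 100/k, design effect DE = 1 + (m − 1) × ICC, SE = 1.5 × √(2 × DE/100), and a noncentral t with 2(k − 1) degrees of freedom:

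- k = 4, ICC 0.01: m = 25, DE = 1.24, SE = 0.236, 0.8/SE = 3.39, df = 6, power 80.4%.
- k = 10, ICC 0.005: m = 10, DE = 1.045, SE = 0.217, 0.8/SE = 3.69, df = 18, power 93.7%.

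The stated range of about 80% to 94% is reproduced. It contains no allowance for contamination.

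**Illustrative dilution**

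Let c be the share of the session's effect that control men, on average, also receive. The contrast becomes 0.8 × (1 − c). The documents give no value for c, so every row below the first is an assumption.

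| c | Difference (points) | Power, k = 4, ICC 0.01 | Power, k = 10, ICC 0.005 |
|---|---|---|---|
| 0 | 0.80 | 80.4% | 93.7% |
| 10% | 0.72 | 72.0% | 88.1% |
| 20% | 0.64 | 62.0% | 79.7% |
| 30% | 0.56 | 51.2% | 68.5% |

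c is the proportion of control men reached times the strength of what reaches them relative to the full session. For c = 20%, every control man would need exposure one fifth as strong as the session. The 0.8 points also come from a 10-point scale, whereas B.4.c uses a 17-item one. The table shows sensitivity and is not a forecast. No comparable figure can be given for selective recruitment.

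Separately, the design has 2 neighborhoods per group, not 4 to 10. The same formula with k = 2 gives 40% to 46% with no contamination at all. That is a different and larger problem.

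**The case against.** A reader might infer that the plan puts prostate publicity into control neighborhoods and so distorts Hypotheses 3a and 3c and Aim 4. The documents do not support that, for these reasons:

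- The list in B.3.b is optional. Use at control sites is permitted, not established.
- The same-day knowledge contrast is largely protected. It spans a session of about 15 minutes, with surveys on either side.
- The control booklet's screening topic is not shown to include prostate. B.4.c lists prostate screening options and guidelines for the intervention session only. Training every educator on prostate cancer does not show that it is taught to controls.
- Aim 4 only observes screening rates and has no hypothesis. A narrowed descriptive contrast is the most that could follow.
- The plan does not call for early online release of the prostate video. B.3.b describes a format suited to uploading, and B.4.f places internet release under dissemination at the end of the project.
- The documents describe no condition-specific recruitment. If it occurred, the baseline measures and the confounder adjustment in B.4.d would capture much of prior interest.

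All of this stands, and it limits the claim to a conditional one. It does not close the gap. The publicity is unassigned, both ways of assigning it carry a cost, and B2.f addresses neither. Baseline adjustment is partial because it cannot correct for exposure during follow-up or for differences that were not measured.

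**Conclusion.** The concern holds in conditional form. The plan permits prostate-branded publicity at partner sites and online without separating conditions, and its one contamination safeguard does not reach it. Shared use could narrow the contrasts in knowledge, norms, intention and decision making at 1 and 4 months, and in the observed screening rates. Use in intervention neighborhoods alone could make the groups differ in ways that adjustment only partly corrects. The same-day knowledge contrast is least at risk.

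The size is unknown. The 0.72 to 0.56 points at 10% to 30% dilution rest on an assumed rate, and on a dilution that a button or poster alone may not produce. The change is worth making before materials are produced, because exposure cannot be undone afterwards.

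**What to change.** - **B.3.b and B.4.a:** use one condition-neutral men's health brand for buttons, posters, flyers, e-mail and the web page in all four neighborhoods. Hold prostate-branded public material until the last 4-month survey is complete. State the same for online posting of the prostate video, which makes the timing implied by B.4.f explicit.
- **B.4.c:** state that the cancer-screening topic in the control booklet covers non-prostate cancers. Have educators take prostate questions in control sessions after the same-day endpoint survey, and put this in the training manual.
- **Unchanged:** consent content, and referral to screening for both groups. Withholding the session topic until after baseline is not recommended. The baseline survey itself asks about prostate cancer, so little would be gained, and it would raise a consent issue.
- **Optional:** an item on prostate messages seen or heard, in the 1- and 4-month surveys, would give the missing exposure rate.

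The cost is wording changes and a short educator instruction before production. The real downside is somewhat less eye-catching recruitment material, in a study that expects to screen about 2,000 men to enroll 200 (B.4.a).
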